- country,
- any past prior use (yes or no) of any oral antidiabetic medication,
- baseline HbA1c category [$\leq 8.5\% (\leq 69 \text{ mmol/mol})$ or $> 8.5\% (> 69 \text{ mmol/mol})$],
- and baseline measurement as a covariate.

For analyses with HbA1c, the baseline HbA1c category will not be included in the model. An unstructured covariance structure will model the relationship of within-patient errors.

The Kaplan-Meier method will be used for estimation of cumulative event-free survival rates over time, and cox proportional hazards regression analysis will be used to compare hazard rates among treatments.

Summary statistics for categorical measures (including categorized continuous measures) will include sample size, frequency, and percentages. Fisher's exact test will be used to examine the treatment difference in categorical outcomes. Logistic regression may be used to examine the treatment difference in binary efficacy outcomes. The negative binomial regression model will be used for the treatment comparison of discrete count measures if deemed appropriate.

Other statistical methods may be used, as appropriate, and details will be documented in the SAP.

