6.12.2.2. Proportion of Patients Achieving HbA1c<7% and <5.7% at the 40 Week Visit

The analysis relative to the “efficacy” estimand for the endpoint at 40 weeks will be performed using EAS with missing values imputed from an MMRM model and then dichotomized. The MMRM model includes treatment, stratification factors, visit, and treatment-by-visit interaction as fixed effects, and baseline HbA1c as a covariate. After dichotomizing continuous HbA1c, the

data is analyzed using a logistic regression model with treatment, country/pooled country, past use of OAM as fixed effects, and baseline HbA1c as a covariate. In addition, analysis will be conducted utilizing data using EAS from baseline through the 40-week visit with the aid of a longitudinal logistic regression with repeated measurements with country/pooled country, past use of OAM, treatment, visit, treatment-by-visit interaction as fixed effects, and baseline HbA1c as a covariate. In case longitudinal logistic model does not converge due to small number of events, logistic regression will be utilized to analyze proportion of patients achieving HbA1c<7% at nominal visits.

Analysis relative to “treatment-regimen” estimand will be conducted by utilizing HbA1c data in FAS at baseline and at the 40-week visit with the aid of a logistic regression with multiple imputation of missing HbA1c data at the 40-week visit (see Section 6.12.1.3 for details). Model terms will include treatment, country/pooled country, past use of OAM as fixed effects, and baseline HbA1c as a covariate and statistical inference over multiple imputations will be guided by Rubin (1987).

Similar analyses will be performed for proportion of patients achieving HbA1c <5.7%.

6.12.3. Type 1 Error Rate Control Strategy for Primary and Key Secondary Efficacy Analysis

Since they are intended for different purposes, no type 1 error rate adjustments will be made for conducting analysis relative to “efficacy” and “treatment-regimen” estimands. For analysis within each estimand, type 1 error rate control strategy for evaluation of primary and key secondary objectives is illustrated in [Figure GPGK.6.1](#). The type I error rate control strategy for the Pharmaceuticals and Medical Devices Agency (PMDA) is in [Appendix 1](#).

The primary and key secondary objective hypotheses are as follows,

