- $H_{5,1}, H_{10,1}$, and $H_{15,1}$: Superiority test of tirzepatide 5 mg, 10 mg, 15 mg versus placebo in HbA1c change from baseline at 40 weeks respectively.
- $H_{5,2}, H_{10,2}$, and $H_{15,2}$: Superiority test of tirzepatide 5 mg, 10 mg, 15 mg versus placebo in body weight change from baseline at 40 weeks respectively.
- $H_{5,3}, H_{10,3}$, and $H_{15,3}$: Superiority test of tirzepatide 5 mg, 10 mg, 15 mg versus placebo in proportion of patients achieve HbA1c<7% at 40 weeks respectively.
- $H_{5,4}, H_{10,4}$, and $H_{15,4}$: Superiority test of tirzepatide 5 mg, 10 mg, 15 mg versus placebo in fasting serum glucose (FSG) change from baseline at 40 weeks respectively.
- $H_{5,5}, H_{10,5}$, and $H_{15,5}$: Superiority test of tirzepatide 5 mg, 10 mg, 15 mg versus placebo in proportion of patients achieve HbA1c<5.7% at 40 weeks respectively.

$H_{5,1}$, $H_{10,1}$, and $H_{15,1}$ will be initially tested each at 0.01667 significance level. A graphical testing scheme (Bretz et al. 2009, 2011) presented in [Figure GPGK.6.1](#) will be used to strongly control for type 1 error.

[figure not shown]

Figure GPGK.6.1. Type 1 error control strategy for primary and key secondary efficacy endpoints.

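### The Week 40 logistic test of HbA1c <5.7% has no method for a placebo arm with no responders, so a Wald or Rubin-pooled test could miss a large effect at all three doses

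*SAP*

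**What the plan says.** SAP 6.12.3 places H5,5, H10,5 and H15,5 in the controlled family. Each tests one dose "versus placebo in proportion of patients achieve HbA1c<5.7% at 40 weeks respectively", so all three share one placebo arm.

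SAP 6.12.2.2 sets out the method for <7% and carries it over to <5.7% without change.

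- **Efficacy estimand:** Week 40 data have "missing values imputed from an MMRM model and then dichotomized". The "data is analyzed using a logistic regression model with treatment, country/pooled country, past use of OAM as fixed effects", plus baseline HbA1c.
- **Treatment-regimen estimand:** the analysis is done "with the aid of a logistic regression with multiple imputation of missing HbA1c data at the 40-week visit", with inference by Rubin's rules.
- **Fallback:** "In case longitudinal logistic model does not converge due to small number of events, logistic regression will be utilized". This covers only the additional longitudinal model, and it leads to ordinary logistic regression. The SAP revision history describes it the same way.

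Protocol 10.3.3.2 also specifies logistic regression for this endpoint and gives no fallback. Two general provisions are relevant. Protocol 10.3.1 names Fisher's exact test for categorical outcomes and adds that "Logistic regression may be used to examine the treatment difference in binary efficacy outcomes". SAP 6.2 lets an analysis with too few events be replaced by a listing.

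**The concern.** Patients enter with HbA1c between 7.0% and 9.5% on diet and exercise alone (Protocol 6.1). A placebo patient at the bottom of that range must fall by more than 1.3 points to reach <5.7%, so few or no placebo responders is a realistic outcome.

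With none, the maximum-likelihood (ML) log odds ratio for each dose diverges. Its standard error grows faster than the estimate, so the Wald statistic goes to zero however many patients respond on the dose. One empty cell disables all three contrasts. Rubin's rules combine estimates and standard errors, so the pooled test inherits the problem from any imputed dataset with an empty placebo cell.

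Type 1 error is not threatened. What is at stake is power, and the fact that the method deciding three controlled hypotheses would have to be settled after the empty cell had been seen.

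**Working it through.** **The plan's own figure.** The documents give no power or response rate for <5.7%. The stated power of at least 90% for HbA1c change (Protocol 10.1) does reproduce at two-sided 0.017 (critical value 2.387):

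- On-treatment data: 118 × 0.75 = 88.5 versus 118 × 0.65 = 76.7 patients, SD 1.1. SE = 1.1 × √(1/88.5 + 1/76.7) = 0.1716. Power = Φ(0.65/0.1716 − 2.387) = Φ(1.40) = 91.9%.
- All data: 118 versus 118, SD 1.3. SE = 1.3 × √(2/118) = 0.1693. Power = Φ(1.45) = 92.7%.

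**Chance of an empty placebo cell.** P(0) = (1 − p)^n, with p assumed. The 77 are the patients left with on-treatment data if 35% start rescue or stop drug.

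| Assumed placebo rate | n = 118 | n = 77 |
|---|---|---|
| 0.5% | 55% | 68% |
| 1% | 31% | 46% |
| 2% | 9% | 21% |
| 3% | 3% | 10% |

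Alternatively, take p = Φ((5.7 − mean)/SD) with an assumed Week 40 placebo mean of 7.9% to 8.2% and n = 118. P(0) is 42% to 72% at SD 0.9 (assumed), 7% to 25% at SD 1.1 and 0.4% to 4% at SD 1.3. The last two SDs are the protocol's planning values for change in HbA1c.

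**One dataset, 36/118 versus 0/118 (assumed).** Newton-Raphson ML fit, Wald z = estimate/SE:

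- 8 iterations: 8.38/9.17 = 0.91, p = 0.36
- 15 iterations: 15.38/303.7 = 0.05, p = 0.96
- 25 iterations: 25.38/45,076, p > 0.99

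On the same data the ML likelihood-ratio p is 6e-14, Fisher 1e-12 and Firth penalised likelihood ratio 4e-13.

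A simulated four-arm example with country, past OAM use and baseline HbA1c in the model (responders 0, 23, 25 and 29 of 118) gives Wald p = 0.96 for all three doses at 15 iterations. The Firth penalised likelihood-ratio p-values are 6e-9, 2e-9 and 4e-11. In a similar simulation with one placebo responder the Wald test works again (p = 0.0009 at a 20% dose rate).

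**Rubin pooling.** Assume 100 imputations, 36/118 on the dose, and one or two placebo responders in every imputation that is not empty.

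| Empty-cell imputations | ML p, 8 iterations | ML p, 15 iterations | Firth p |
|---|---|---|---|
| 0 | 0.0002 | 0.0002 | 0.00005 |
| 1 | 0.010 | 0.90 | 0.00007 |
| 4 | 0.096 | 0.95 | 0.0002 |

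At 15 iterations one empty cell adds 303.7²/100 = 922 to the pooled variance, so the pooled SE is about √925 = 30.4 against an estimate of 3.71. This needs no observed placebo responder at all, because one observed responder appears in every imputed dataset.

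**Power.** Full enumeration of two binomials, 118 per arm, alpha 0.05/3, ML Wald counted as not rejecting when a cell is empty:

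| Dose rate | Placebo rate | ML Wald | Firth Wald | Firth penalised LR |
|---|---|---|---|---|
| 20% | 0.5% | 45% | 99.6% | 100% |
| 20% | 1% | 69% | 99.6% | 99.9% |
| 20% | 2% | 90% | 99% | 99.5% |
| 20% | 3% | 94% | 97% | 98% |
| 10% | 0.5% | 23% | 43% | 89% |
| 10% | 1% | 33% | 46% | 80% |
| 10% | 2% | 34% | 40% | 60% |

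ML Wald power cannot exceed 1 − P(0), for example 1 − 0.55 = 45%. Type 1 error of the Firth penalised likelihood-ratio test at common rates of 1%, 2%, 3% and 5% is 0.0008, 0.006, 0.010 and 0.013, all below 0.0167.

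**The case against.** **An empty cell may be unlikely.** The placebo rates are assumed, and the normal-model range of 0.4% to 72% is wide. At the protocol's SD of 1.3 for all data it is only 0.4% to 4%, and that is the treatment-regimen setting where Rubin pooling applies. Post-rescue values may add responders too. This stands and limits the priority, but at SD 1.1 the chance is still 7% to 25%.

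**The SAP never says Wald.** For the efficacy estimand a likelihood-ratio test would detect the effect. That is correct, but the SAP does not specify that test either, and Rubin pooling is Wald-type by construction.

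**General provisions exist.** Fisher's test in Protocol 10.3.1 could be invoked, but Protocol 10.3.3.2 assigns logistic regression to this endpoint. Fisher's test is also unadjusted and has no defined pooling over imputations. The listing in SAP 6.2 yields no p-value.

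**The size depends on software settings.** At 8 iterations one empty-cell imputation gives p = 0.010, which still rejects at 0.01667. That is true, but a result that turns on an iteration limit is itself a reason to name the method.

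**The tirzepatide rates are chosen.** The minimum planned effect of 0.65, with an assumed placebo mean of 8.0% and SD 1.1, implies Φ((5.7 − 7.35)/1.1) = Φ(−1.5), about 7%. Power at such rates is limited for any method. At 10%, Firth still has the higher power.

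**Pooled Firth is Wald-type and conservative.** This also stands: 12/118 versus 0/118 in every imputation gives p = 0.022, against 0.0004 for Fisher. Unpooled Firth Wald nevertheless has higher power than ML Wald in every row above.

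**Conclusion.** The concern holds. The plan gives no usable method for H5,5, H10,5 and H15,5 if the placebo arm has no responder. In that event a Wald or Rubin-pooled ML test can fail to reject a very large difference at all three doses.

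The loss is power on one key secondary endpoint and is conditional on the empty cell. It ranges from large at a placebo rate of 0.5% (45% against 100% at a 20% dose rate) to small at 3% (94% against 98%).

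These sizes rest on assumed response rates, 100 imputations and alpha 0.01667. The SAP states that level only for the HbA1c-change hypotheses, and the testing graph is not shown, so any effect on other hypotheses cannot be computed. The point should be fixed; confidence is medium because the placebo rate is unknown.

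**What to change.** Before unblinding, add to SAP 6.12.2.2:

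> For HbA1c <5.7% at Week 40, Firth penalised logistic regression with the same model terms is used for both estimands. Efficacy estimand: penalised likelihood-ratio p-value. Treatment-regimen estimand: the Firth log odds ratio and SE from each imputed dataset, pooled by Rubin's rules.

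The longitudinal fallback sentence can stay. Using Firth throughout, rather than only when a cell is empty, avoids a switch of method that depends on the data. An unpooled Wald risk difference should not be substituted, because its placebo variance is zero when the cell is empty.

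The cost is the SAP wording, a Firth option in the existing logistic programs and a short step for the penalised likelihood-ratio p-value. The odds ratio is slightly shrunk (36/118 versus 2/118: log odds ratio 3.24 becomes 3.03). The pooled Firth test remains conservative when responders are few.

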6.12.4. Other Secondary and Exploratory Efficacy Analyses

Other secondary and exploratory efficacy measures will be summarized by treatment and nominal visit. Unless otherwise specified, missing data will not be imputed and assessments are not subject to type 1 error rate control. See [Table GPGK.6.2](#).

Table GPGK.6.2. Secondary and Exploratory Efficacy Analyses not Controlled for Type I Error

Objective	Relative to the efficacy measure:	Analysis Conducted in a manner similar to:	Additional Information
To compare tirzepatide 5 mg, 10 mg, and 15 mg to placebo	Change from baseline in 7-point self-monitored blood glucose (SMBG) profiles	6.12.1	Use baseline HbA1c strata as a fixed effect in place of baseline HbA1c as a covariate. Use baseline SMBG as a covariate. LSM estimates will be summarized by treatment and 7-points. In addition to the analyses on each of the 7-points, similar analyses will be done for the 2-hour morning, midday, and evening meal excursions, the mean of all meals 2-hour excursion, the mean of all 7-point measurements, the mean of all pre-meal measurements, and the mean of all 2-hour postprandial measurements.
	proportion of patients achieving an HbA1c target value of $\leq 6.5\%$ (48 mmol/mol)	6.12.2.2	None
	proportion of patients achieving an HbA1c target value of $< 8\%$ (64 mmol/mol)	6.12.2.2	None
	proportion of patients who achieved weight loss of $\geq 5\%$, from baseline	6.12.2.2	Use baseline HbA1c strata as a fixed effect in place of baseline HbA1c as a covariate and baseline weight as a covariate
	proportion of patients who achieved weight loss of $\geq 10\%$ from baseline	6.12.2.2	Use baseline HbA1c strata as a fixed effect in place of baseline HbA1c as a covariate and baseline weight as a covariate
	proportion of patients who achieved weight loss of $\geq 15\%$ from baseline	6.12.2.2	Use baseline HbA1c strata as a fixed effect in place of baseline HbA1c as a covariate and baseline weight as a covariate

Secondary and Exploratory Efficacy Analyses not Controlled for Type I Error

Objective	Relative to the efficacy measure:	Analysis Conducted in a manner similar to:	Additional Information
	Change from baseline in waist circumference	6.12.1	Use baseline HbA1c strata as a fixed effect in place of baseline HbA1c as a covariate. Use baseline waist circumference as a covariate.
	Change from baseline in BMI	6.12.1	Use baseline HbA1c strata as a fixed effect in place of baseline HbA1c as a covariate. Use baseline BMI as a covariate.
	Percentage change in body weight	6.12.1	Use baseline HbA1c strata as a fixed effect in place of baseline HbA1c as a covariate. Use baseline body weight as a covariate.
	Change from baseline in fasting glucagon, c-peptide, insulin level, HOMA-B, HOMA-S, and HOMA-IR	6.12.1	Use baseline HbA1c strata as a fixed effect in place of baseline HbA1c as a covariate. Use corresponding baseline parameter as a covariate. Analysis will be based on log transformed measure.
	Change from baseline in lipid parameters (Total-Cholesterol, HDL-C, VLDL-C, TG, LDL-C)	6.12.1	Use baseline HbA1c strata as a fixed effect in place of baseline HbA1c as a covariate. Use corresponding baseline lipid parameter as a covariate. Analysis will be based on log transformed measure.
	Change from baseline in patient reported outcomes: APPADL, EQ-5D-5L, and IW-SP	6.12.1.2	Use baseline HbA1c strata as a fixed effect in place of baseline HbA1c as a covariate. Use corresponding baseline patient outcome score as a covariate.
To characterize efficacy (beyond the end of treatment) with tirzepatide 5 mg, 10 mg, and 15 mg	Change from baseline in HbA1c, body weight	6.12.1	The analysis will be conducted utilizing HbA1c (body weight) data from baseline through the end of follow-up (44 weeks)

Abbreviations: APPADL = Ability to Perform Physical Activities of Daily Living Questionnaire; BMI = body mass index; EQ-5D-5L = 5-level EQ-5D version; HbA1c = hemoglobin A1c; HDL-C = high-density lipoprotein cholesterol; HOMA-B = homeostatic model assessment for β -cell function; HOMA-IR = homeostatic model assessment for insulin resistance; HOMA-S = homeostatic model assessment for insulin sensitivity; IW-SP = Impact of Weight on Self-Perceptions Questionnaire; LDL-C = low-density lipoprotein cholesterol; VLDL-C = very-low-density lipoprotein cholesterol; TG = triglycerides.

6.13. Safety Analysis

Unless specified otherwise, safety assessments will be based on the SS (see [Table GPGK.6.1](#)). All events that occur between the date of first dose of study drug to the date of patient's safety

follow-up visit or patient's end of study participation will be included. For assessing benefit and risk profile through 40-weeks, selected safety analyses may be conducted by utilizing safety data from first dose through the date of 40-week visit. For rare events (<10 patients have the events), summary tables may not be generated, and individual patient level data will be listed.

Unless specified otherwise, comparisons of tirzepatide doses to placebo will be performed.

For selected continuous safety parameters, difference among treatment mean change from baseline at scheduled visits will be assessed via a MMRM using REML. The model will include country/pooled country, baseline HbA1c ($\leq 8.5\%$, $>8.5\% [\leq 69, >69 \text{ mmol/mol}]$), past OAM use (Yes or No), treatment group, visit, and treatment-by-visit interaction as fixed effects, and baseline value of the safety parameter as a covariate. To model the covariance structure within patients, the unstructured covariance matrix will be used. If this model fails to converge, the covariance structures specified in Section 6.12.1.1 will be tested in order.

For selected safety parameters, time-to-first-event analysis via cox-proportional hazards model may be conducted. For patients experiencing an event, "time-to-first-event" will be the time (in weeks) to the first occurrence of the event. For patients without the event, "time-to-event" will be censored at end of study participation (study discontinuation, safety follow-up visit, or date of death).

Where specified, rate of events will be analyzed using a generalized linear mixed-effects model assuming the number of events follow a negative binomial distribution, and with treatment as a fixed effect. The logarithm of years in specified time interval will be adjusted as an offset to account for possible unequal treatment duration in specified time interval between patients.

6.13.1. Adverse Events

A treatment-emergent adverse event (TEAE) is defined as an event that first occurred or worsened in severity after the first dose. The MedDRA Lowest Level Term (LLT) will be used in the treatment-emergent derivation. The maximum severity for each LLT during the baseline period including ongoing medical history will be used as baseline severity. For events with a missing severity during the baseline period, it will be treated as 'mild' in severity for determining treatment-emergence. Events with a missing severity during the postbaseline period will be treated as 'severe' and treatment-emergence will be determined by comparing to baseline severity.

The percentages of patients with TEAEs will be summarized by treatment using MedDRA PT nested within SOC. Statistical comparisons will be applied at both the SOC and PT levels. Events will be ordered by decreasing frequency within SOC, with the SOC in alphabetical order. For events that are sex-specific, the denominator and computation of the percentage will include only patients from the given sex.

Overview of the number and percentage of patient who experienced a TEAE, serious adverse event (SAE), death, discontinued from study treatment due to an AE, discontinued from study due to an AE, as well as relationship to study drug, will be summarized by treatment.

The percentages of patients with TEAEs, overall and common (common TEAEs occurred in $\geq 5\%$ of patients before rounding), will be summarized by treatment using MedDRA PT. Events will be ordered by decreasing frequency.

The percentages of patients with TEAEs by maximum severity will be summarized by treatment using MedDRA PT. For each patient and TEAE, the maximum severity for the MedDRA PT is the maximum postbaseline severity observed from all associated LLTs mapping to the MedDRA PT. The maximum severity will be determined based on the non-missing severities. If all severities are missing for the defined postbaseline period of interest, it will show as missing in the table. Only counts and percentages will be included for the TEAEs by maximum severity.

Patient narratives will be provided for all patients who experience any of the following “notable” events:

- deaths
- serious adverse events
- pregnancy
- permanent discontinuations of study treatment due to AEs
- severe adverse events of special interest

Patient narratives will be provided for patients who experience severe AESI as well.

6.13.1.1. Deaths

A listing of all deaths will be provided. Listing will include patient identification including the treatment, site number, date of death, age at the time of enrollment, gender, MedDRA PT of associated AE, time from first dose of study drug to death, time from last dose of study drug to death (if patient had discontinued study drug), cause of death as reported by investigator, caused of death as adjudicated by Clinical Endpoint Committee (CEC).

6.13.1.2. Other Serious Adverse Events

The number and percentage of patients who experienced an SAE (including deaths and SAEs temporally associated or preceding deaths) during the study will be summarized by treatment using MedDRA PT nested within SOC. Events will be ordered by decreasing frequency within SOC.

A listing of all SAEs will be provided. Listing will include and not limit to treatment, patient identification including the site number, treatment group, date of event, age at the time of enrollment, gender, MedDRA SOC and PT, severity, action taken, outcome, relationship to study drug, time from first dose of study drug to the event, and event duration.

6.13.1.3. Discontinuation From Study Due to Adverse Event

The number and percentage of patients who prematurely discontinue the study due to an AE will be summarized by treatment using MedDRA PT nested within SOC. Events will be ordered by decreasing frequency within SOC.

